9.4 Criteria for Intervention and Discontinuation

The administration of study drug may be discontinued by the PI or designee if they no longer consider it in the participant's best interest to continue in the study, for example, SAE, clinical reasons, or if a patient is entered onto the palliative care pathway. The study intervention will also be discontinued if the participant or their representative requests it. Should the study drug be discontinued, the participant will continue to be followed for safety purposes (up to 30 days of date of randomisation) and participants will remain in the study for follow-up purposes unless they decline follow-up. If the study treatment is discontinued and the participant is willing to undergo follow-up, these will be performed as outlined previously.

Where patients do not wish to undergo further assessments, information relating to safety will be obtained from the participant's clinical records. We will retain and analyse all information obtained up to the point of withdrawal on an intention to treat basis. This will be explained in the participant information sheet and outlined at study entry.

The study will be discontinued in the event that new information comes to light that would make the findings of the study obsolete, if there are changes to the study infrastructure which mean that the study can no longer feasibly be completed or if there are serious safety concerns. Otherwise, it is anticipated that the study will continue until completion.

9.5 Notification of Deaths

All deaths that occur within 30 days of the date of randomisation will be reported as SAE as per pharmacovigilance section to the Manchester CTU. This report will be within 24h of the research team becoming aware. In addition, all deaths will be recorded in the CRF up to 6 months post randomisation.

9.6 Pregnancy Reporting

The demographic profile of aSAH is such that the incidence is double in females than in males. For this reason, women of child-bearing potential (WOCBP) will be included in the trial. There are limited data from the use of IL-1Ra in WOCBP. However, reproductive studies have been conducted with IL-1Ra on rats and rabbits at doses up to 100 times the human RA dose and have revealed no evidence of impaired fertility or harm to the foetus. IL-1Ra is not recommended during pregnancy and in women of childbearing potential not using contraception. It is unknown whether IL-1Ra/metabolites are excreted in human milk. A risk to the newborns / infants cannot be excluded so breast-feeding should be discontinued during treatment with IL-1Ra. Great effort will be made to ensure that female participants who are pregnant or breast feeding will be identified at screening and excluded from study participation.

The Investigator must ensure that all participants are fully aware at the start of a clinical trial of the importance of reporting all pregnancies that occur whilst being treated with the study drug and occurring up to 30 days post randomisation. This should be done as part of the consent process by explaining clearly to the participants or the participant representative of the potential dangers of being or becoming pregnant.

WOCBP enrolled in the study will only be administered IL-1Ra while being an in-patient. Moreover the half-life of SC IL-1Ra is 4-6 hours. It is therefore very unlikely that such participants will become pregnant while being exposed to the study drug. Nevertheless WOCBP will be informed of the lack of safety data on the use of IL-1Ra in pregnancy and strongly advised to avoid becoming pregnant during their in-patient participation.

No safety concerns on the use of IL-1Ra in male RA or CAPS patients with partners of childbearing potential have arisen since its introduction for clinical use, therefore no contraceptive requirements will be put in place for male participants.

Any pregnancy occurring in a participant during treatment or within 30 days of randomisation must be reported to the *Manchester CTU by* email ([contact]) immediately but no later than 24 hours of the site staff becoming aware of it using a Pregnancy Notification Form. Study drug will be stopped immediately. It is the Investigator's responsibility to obtain consent for follow-up from the participant.

The Manchester CTU will follow-up all pregnancies for the pregnancy outcome via the Investigator, using a Pregnancy Outcome Form. The Manchester CTU will then inform the sponsor and manufacturer within one working day of receipt. The Manchester CTU will work with the investigator to ensure that all relevant information is provided to the sponsor and manufacturer. Should a pregnancy occur during the trial, the Investigator should offer counselling to the participant, and discuss the risks of continuing with the pregnancy and the possible effects on the foetus. Monitoring of the participant and the baby should continue until the conclusion of the pregnancy. Pregnancy is not considered an AE unless a negative or consequential outcome is recorded for the mother or child/foetus. If the outcome meets the serious criteria, this would be considered an SAE.

9.7 Overdose Reporting

Administration of study drug is restricted to research staff delegated the responsibility by the PI or appropriately trained ward nurses. Participants will receive two injections of 100mg study drug / placebo via a subcutaneous syringe each day. Injections must be a minimum of 8 hours and maximum of 16 hours

apart. Participants are allocated treatment kits and the procedure to show proof of administration and drug reconciliation make accidental overdose highly unlikely.

Accidental overdose will be reported to the Manchester CTU by the completion of the Overdose CRF page. The completed Overdose CRF page should be reported to the *Manchester CTU by* email ([contact]) immediately, but no later than 24 hours of the investigator or site staff becoming aware. The Manchester CTU will then inform the sponsor and manufacturer within one working day of receipt. The Manchester CTU will work with the investigator to ensure that all relevant information is provided to the sponsor and manufacturer.

Participants will continue study participation. No adverse effects are anticipated for an accidental overdose.

9.8 Urgent Safety Measures

If any urgent safety measures are required the CI/Sponsor will contact the MHRA's Clinical Trial Unit to discuss the issue with a safety scientist. Ideally within 24 hours but no later than 3 days from the date the measures are taken, the Sponsor will send written notice to the MHRA and the relevant REC of the measures taken and the circumstances giving rise to those measures. Written notification in the form of a substantial amendment will also be submitted to MHRA within 7 days. If an urgent safety measure is implemented at site the Manchester CTU should be notified immediately by emailing [contact]. The Manchester CTU will also notify all recruiting centres within 24 hours of the measures being imposed.

9.9 New Safety Findings

If a new safety finding emerges from sources such as study drug manufacturers, data analysis or IDMC findings, the CI will review the finding for its impact on the subjects participating in the relevant trial(s). If there is a potential impact on trial participants' safety, the Manchester CTU will take appropriate action in conjunction with the Sponsor, CI and research team. Appropriate reporting mechanisms are followed in the event of actions being taken.

9.10 The type and duration of the follow-up of subjects after adverse events

All study participants who experience an adverse event will be followed-up until resolution or stabilisation. If an event is identified as potentially related to study drug at day 30 assessment, further contact will be made with the participant until the event is resolved. Resolution reports will be sent to the Manchester CTU within 7 days of the recruiting centre becoming aware. Should an Investigator become aware of any drug-related SAEs after the patient's 30 day assessment, these must also be reported to the Manchester CTU within the expedited timelines stated above.

9.11 Periodic Safety Reports

9.11.1 Development safety update reports (DSUR)

The Manchester CTU will submit a development safety update report (DSUR) to the MHRA within 60 days of the Developmental International Birth Date (DIBD) of the trial each year until the trial is declared ended by the Manchester CTU on behalf of the Sponsor.

9.11.2 Annual progress reports (APR)

The Manchester CTU will submit an annual progress report (APR) to the REC within 30 days of the anniversary date on which the favourable opinion was given, and annually until the trial is declared ended.

10. TRIAL MANAGEMENT AND OVERSIGHT ARRANGMENTS

10.1 Roles and Responsibilities

10.1.1 Trial sponsor

The trial will be Sponsored by the University of Manchester. The responsibilities of the Sponsor are as defined in 9.10 of the UK Policy Framework for Health and Social Care Research, V3.3. In line with this requirement, the Chief Investigator will ensure that all involved in the research project understand and discharge their responsibilities in accordance with the agreed protocol and any relevant management, ethical and regulatory approvals.

Responsibilities of the Sponsor are detailed in University of Manchester Policy for Compliance with The Medicines for Human use (Clinical Trials) Regulations 2004 and subsequent amendments (Investigational Medicinal Products) UM/10/POL/CT003. The University of Manchester as the Sponsor has delegated a number of these responsibilities as detailed in the Delegation of Responsibilities section of the research agreement signed between the Sponsor and Manchester CTU. The Sponsor has legal responsibilities that cannot be delegated.

10.1.2 Manchester CTU

Full details of the role and responsibilities of the Manchester CTU are outlined in the Delegation of Responsibilities section of the research agreement signed between the Sponsor and Manchester CTU.

Trial Management:

Provision of trial management activities, including but not limited to, provision of expert advice on the Study Protocol design, development of protocol and other study documentation, preparation of regulatory submissions and reporting, co-ordination with sponsor, study lifecycle project management, management of safety reporting, preparation and maintenance of essential documents (including amendments) in accordance with GCP, management of study monitoring activities and co-ordinate study close-out.

Data management:

Provision of data management activities, including but not limited to, provision of expert advice on the Study Protocol design, study risk assessments, design of CRF and study database and CRF completion guidelines, study database testing, production of data validation guidelines and attendance at relevant Chief Investigator meetings.

Data review and validation of data, raising data queries for resolution, liaison with Study Sites with regard to clinical trials data and data queries, provision of relevant data for IDMC meetings and reports, data QC if required and provision of data for statistical analysis. Provision of expert advice on any Study Protocol amendments relating to data aspects.

Quality Assurance & Pharmacovigilance:

Provision of QA/QC activities in connection with data capture, verification and relevant supporting documentation. Maintenance of relevant Manchester CTU standard operating procedures.

Review of relevant clinical trial documentation, including relevant GCP essential documents (source document verification).

Contractual Arrangements:

To put in place the necessary Study Site agreements with the relevant organisations as set out in the Protocol or otherwise agreed.

10.1.3 Funder

The trial is funded by the National Institute for Health Research. The roles and responsibilities of the funder are defined in the investigator-sponsor study (ISS) agreement.

10.2 Oversight Committees

10.2.1 Trial Management Group (TMG)

A Trial Management Group (TMG) will be established and will include those individuals responsible for the day-to-day management of the trial including the Chief Investigator, co-investigators and identified collaborators, Principal Investigators, sponsor pharmacist, the trial statistician and Manchester CTU trial manager(s), data manager(s) and monitor(s). Notwithstanding the legal obligations of the Sponsor and Chief Investigator, the TMG have operational responsibility for the conduct of the trial including monitoring overall progress to ensure the protocol is adhered to and to take appropriate action to safeguard the participants and the quality of the trial.

The TMG will meet to discuss progress at least quarterly once the trial is actively recruiting. Minutes will be taken at TMG meetings and copies of the minutes will be filed in the Trial Master File. The trial manager and CI will ensure that all relevant issues and actions discussed during the meeting are followed up and resolved and details of significant issues will be made available to participating sites. Minutes of all TMG meetings are available on request.

10.2.2 Trial Steering Committee (TSC)

A Trial Steering Committee (TSC) will be established and will include an independent Chair (not involved directly in the trial other than as a member of the TSC), not less than two other independent members, a representative from a consumer group, plus the CI, and a statistician. The role of the TSC is to take responsibility for the scientific integrity of the trial, the scientific validity of the trial protocol, assessment of the trial quality and conduct (to ensure that the trial is being conducted in accordance with the principles of GCP and the relevant regulations) as well as for the scientific quality of the final study report. Decisions about the continuation or termination of the trial or substantial amendments to the protocol are usually the responsibility of the TSC.

The TSC will meet once ethics approval has been given and before the trial begins recruitment. Once the trial has started the TSC should meet at least every 6 months annually to monitor the progress of the trial although there may be periods when more frequent meetings are necessary. Meetings should be organised by the CI via the CTPM. Minutes will be taken at TSC meetings and copies of the minutes will be filed in the Trial Master File and made available to the Sponsor. The trial manager and CI will ensure that all relevant issues and actions discussed during the meeting are followed up and resolved and details of significant issues will be made available to participating sites. Minutes of all TSC meetings are available on request. The Committee's terms of reference, roles and responsibilities will be defined in a charter issued by the Manchester CTU.

10.2.3 Independent Data Monitoring Committee (IDMC)

An IDMC will be instituted to review accruing trial safety data and to assess whether there are any safety issues that should be brought to the participants' attention, whether any safety amendments should be made or if there are any reasons for the trial to discontinue. The IDMC will be independent of the investigators, funder and sponsor. The CI and TMG with the support of the Manchester CTU will be responsible for nominating IDMC members.

The Committee's terms of reference, roles and responsibilities will be defined in a charter issued by Manchester CTU. This charter will outline any stopping rules and the frequency of analysis and IDMC meetings during the trial. The IDMC will receive a monthly report detailing all life threatening or SAEs resulting in death and the IDMC Chair will also receive the total numbers of SAEs in order to expedite a safety review if more SAEs are being seen than would be expected. A cumulative review of all unblinded safety information will occur on a 12 monthly basis.

Reports to the IDMC will be prepared and presented by the trial statistician and CTPM prior to the IDMC meeting. In these reports all infections will be grouped together rather than assigned to body systems. The IDMC Chair will then report their recommendations to the Chair of the TMG and may request additional reports or information if required. This report will be submitted to the TMG, and if required, the HRA and the MHRA and the CI and CTPM will ensure that all actions and recommendations are followed up.

Prior to scheduled review of safety data, the unblinded allocation list will be supplied to the members of the Data Monitoring Committee by the randomiser using confidential email.

For statistical analysis purposes, the confidential section of reports to the IDMC will be unblinded by merging the participant database with the randomisation schedule. Only the statistician undertaking the analyses and the IDMC members will have sight of these reports. At the end of data collection the validated participant data will be merged with the randomisation schedule to create a locked analysis dataset. Validation of the allocation by comparison with IL1-Ra at day 3-5 will be undertaken at this stage.

11.2 Planned Recruitment Rate

The trial will recruit 1000 participants over 42 months. We have based our calculations on the recruitment rate into our own phase II study (3 centres), recruitment into the STASH trial¹⁴, and numbers recorded in national audit data (https://www.hope-academic.org.uk/uksah).

Our calculations distinguish 8 'category A' sites each anticipated to recruit two participants per month, 6 'category C' sites each recruiting one participant per month, and 6 intermediate, 'Category B', sites. We have allowed a two-month 'run-in' phase at each site with 50% of target recruitment and assumed opening of one new site per month.

11.3 Statistical Analysis Plan

A detailed statistical analysis plan will be confirmed with the Trial Steering Committee prior to the study's end and pre-tested using a randomly generated indicator variable in place of "allocation". A summary of the approach is presented below.

11.3.1 Summary of baseline data and flow of patients

The following variables will be presented to demonstrate the extent of comparability between the randomised groups:

Age

Sex

WFNS grade

Time since ictus (completed days)

A CONSORT flow chart (http://www.consort-statement.org/) will be used to show the participant flow with reasons (where known) for discontinuation.

11.3.2 Primary outcome analysis

Primary analysis will apply proportional odds regression to the mRS at 6 months with adjustment for the stratification criteria. The adjusted odds ratio will be presented with 95% confidence interval.

11.3.3 Secondary outcome analysis

Secondary outcomes will be assessed for the same population using logistic and linear regression methods with similar adjustment. Safety analyses up to 30 days will be undertaken in both the aSAH population and the full randomised cohort.

11.3.4 Mechanistic analysis

As mechanistic mediation analysis is not currently developed for ordinal outcomes we will apply the sliding dichotomy approach to our primary outcome⁴⁵. We will then adopt the parametric modelling approach of counter-factual direct and indirect effects [STATA 'paramed' command] to assess the causal relationship between IL-6 and clinical outcome.

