1.1.2 Inflammation in aSAH

Inflammation is a key factor following aSAH associated with vasospasm, oedema and neuronal loss. There is now both experimental and clinical evidence that inflammation is a major contributor to brain injury and ischaemia and holds significant promise as a therapeutic target¹³. A number of potential anti-inflammatory strategies have been suggested or trialled in aSAH⁸, including clazosentan and cilostazol, but none have shown the anti-inflammatory activity of IL-1Ra or have its extensive preclinical data. Statins have an anti-inflammatory activity and have been trialled recently, most notably in the recent STASH study, but showed no evidence of clinical effectiveness¹⁴; it is of note that statins in this study did not reduce the inflammatory mediator C-reactive protein (CRP)¹⁵ which contrasts with our proposed intervention.

Interleukin-1 (IL-1) is a pro-inflammatory cytokine that is produced in response to brain injury and triggers a cascade of events that leads to further pro-inflammatory cytokine expression, increased vascular activation, increased numbers of circulating leucocytes, activation of glial mediated neuronal toxicity and increased neuronal excitability¹³. The naturally occurring antagonist of IL-1, interleukin-1 receptor antagonist (IL-1Ra) blocks these effects by competitively binding to the IL-1 receptor. In experimental SAH, IL-1Ra inhibits the IL-1 α driven inflammation induced partly by haem released from lysed red blood cells¹⁶. A number of clinical studies that demonstrated a correlation between elevated levels of inflammatory markers (including cytokines such as IL-1 and its downstream mediator interleukin-6; IL-6) in cerebrospinal fluid (CSF) of people with aSAH that are related to poor neurological outcome. Plasma CRP is an independent predictor of clinical outcome as measured by the modified Rankin Scale (mRS) in good grade (World Federation of Neurosurgical Societies; WFNS grade 1 and 2) patients¹⁵. Plasma IL-6 levels are also associated with poor functional outcome¹⁷. Plasma inflammatory cytokines may reflect intracerebral processes, or may contribute to brain injury via the damaged blood brain barrier⁸. Rodent studies using bone marrow transplantation indicate that both central and peripherally derived IL-1 are involved in ischaemic brain injury¹⁸.

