7.4 Randomisation

Following consent by the patient or their legal representative and the baseline assessment (including baseline blood sample), the patient will be immediately randomised using an independent, bespoke, online randomisation service to ensure third-party concealment of allocation. This randomisation service will be provided by Glasgow Clinical Trials Unit who will design, programme and maintain the online service for the duration of study. 1:1 randomisation will be stratified by site (because of the potential for differences in surgical and post -operative practices), grade of SAH using WFNS (Grades 1&2 vs 3 to 5) and known aneurysmal status (aneurysm confirmed vs aneurysmal status unknown).

Randomisation takes place on Day 0. The first IMP administration should be given as soon as possible after randomisation and within 72 h of ictus. IMP administration will then continue according to the schedule in section 8.4 for a maximum 21 days from ictus or until discharge from neurosurgical care (whichever is earlier). The following diagram illustrates the day of randomisation in relation to IMP administration and data collection.

Day 0	Day 1	Day 2	Day 3	Day 4	Day 5	Day 6	e.t.c
Randomisation			Day 3-5 B	lood sample collection			
Begin IMP administration	Contin	ue IMP/plac	cebo admini	stration for	a maximum	21 days fror	n ictus

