7.7 Trial Assessments

7.7.1 Pre-randomisation evaluation

At screening, research staff will review patient health records to confirm eligibility according to the eligibility criteria in section 6. This will include basic demographics (age), past clinical history and radiological data. No identifiable participant data will be recorded. An anonymised screening log will be maintained. Following consent, participants will undergo a baseline assessment which will include transcription of source data including baseline research blood sampling, demographics (date of birth, sex, treating centre), and past clinical & medical history (date and time of ictus; World Federation of Neurological Societies (WFNS) grade at first presentation; pre-morbid mRS; pre-morbid risk factors (including smoking, hypertension, diabetes, ischaemic heart disease); existence of pre-morbid anxiety, depression or fatigue). A 10ml baseline blood sample will be taken immediately following consent and before randomisation for measurement of plasma IL-6. Sampling will be undertaken to ensure the minimal inconvenience to the patient and wherever possible blood will be sampled from an established central venous or arterial line. Where possible, research bloods will be taken at the same time as clinical bloods. Clinical reports of renal function and full blood count will be checked by an appropriate member of the PI team prior to randomisation (see exclusion criteria). Additional tests of full blood count, renal function, and liver function will be performed at the discretion of the clinical team as part of the direct clinical care and will be reviewed at the pre-specified post-randomisation evaluations as detailed below.

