7.7.2 Post-randomisation evaluations

Adverse event (AE) reporting checks will be made by a delegated member of the research team at the day 3-5 assessment, between day 10-12, on the final day of study treatment and at day 30 post randomisation. Patients enrolled into the study will also be under continuous clinical observation as part of their routine direct clinical care. The site PI or delegate will liaise with the clinical team on a daily basis and a telephone number will be provided as a direct point of contact with the research team for discussion of any concerns relating to the study or administration of the study drug. Any adverse events noted outside the prespecified reporting checks will be processed.

Details of each administration of study drug will be recorded in the case report form (CRF) and the clinical drug administration record. This will include details of administration site, date and time of administration.

A second research blood sample will be taken at 3-5 days post randomisation for measurement of plasma inflammatory markers (IL-6) (putative mediator) and IL-1Ra concentration (treatment fidelity and validation of randomisation). Further clinical data (survival check; detail of target aneurysm, including confirmation, position and treatment) will be collected at the day 3-5 post randomisation assessment.

On the final day of study treatment another survival check will be performed. As part of the end of treatment assessment the participants will be asked to confirm their willingness to be contacted at 30 days and 6 months of the date of randomisation and contact details of the participants (or next of kin) will be confirmed.

A final AE check and survival check will be performed at 30 days post randomisation on all patients who have received at least one dose of study drug and will be completed by local research staff. To avoid

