7.8 Withdrawal Criteria

Participants without confirmation of aneurysm within 72 hours of randomisation and those patients found to be non-aneurysmal post randomisation will be withdrawn from treatment. If participants are withdrawn for this reason they will continue to be followed up until their safety (30 days post randomisation) assessment. While baseline plasma samples collected from these participants will not be analysed for this trial, the samples will be shipped to the trial centre (see section 7.9) for potential use in future research (provided consent was given for this). If consent was not given for use of samples in future research, the sample must be destroyed at the participating site as per local procedure

In the event of death between randomisation and the diagnosis of aneurysm (usually by CTA), these participants will be excluded as 'Failed To Confirmed Aneurysm' and this event should be reported as detailed in notification of death (section 9.5).

Participants have the right to withdraw from the trial treatment or trial participation at any time, without having to give a reason and without any effects on their clinical care. The withdrawal process will be explained prior to consent.

If a participant is withdrawn from trial treatment, study drug will be stopped immediately and no further blood samples will be obtained. Subsequent assessments of patient safety and an end of study outcome will be completed as planned. All data and samples will be retained and included in analyses. Trial treatment should be stopped for the circumstances listed below.

- Uncontrolled AE/SAE that is related to, or potentially related to, study drug;
- Participant or personal legal representative decision, or at the PI discretion;
- If a severe allergic reaction occurs administration of IL-1Ra should be discontinued and appropriate treatment initiated;
- If participants become neutropenic (ANC <1.5 x 10⁹/l), IL-1Ra treatment should be discontinued;
- Pregnancy;
- Symptomatic deterioration where the investigator feels the participant's receipt of study drug is no longer clinically appropriate;
- Study suspended or stopped for any reason.

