11.5 Adjusted Analysis

All inferential analyses will adjust for the stratification factors used in the allocation routine. Plasma IL-6 and IL-1Ra levels will be log-transformed prior to analysis and presentation.

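### Section 7.8 stops the day 3-5 IL-6 sample at treatment withdrawal for participants who stay in the analysis, and the protocol does not commit baseline IL-6 to the mediation model

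*Protocol*

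**What the plan says.** **The mechanism analysis.** Section 11.3.4 dichotomises the mRS by the sliding method and continues: "We will then adopt the parametric modelling approach of counter-factual direct and indirect effects", using a named Stata command. The aim is a causal statement about IL-6 and outcome. No covariates are listed there. Section 11.5 sets a general rule: "All inferential analyses will adjust for the stratification factors used in the allocation routine". Under section 7.4 these factors are site, WFNS grade in two bands and known aneurysmal status. Section 11.3 describes the text as a summary, with a detailed SAP to follow.

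**The samples.** Section 7.7.1: "A 10ml baseline blood sample will be taken immediately following consent and before randomisation for measurement of plasma IL-6". Section 7.7.2: "A second research blood sample will be taken at 3-5 days post randomisation". The second sample supplies IL-6 as the putative mediator, and IL-1Ra for treatment fidelity and to validate the randomisation.

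**Withdrawal from treatment.** Section 7.8: "study drug will be stopped immediately and no further blood samples will be obtained". The same paragraph keeps safety and end-of-study outcome assessments in place. The listed reasons for stopping include drug-related adverse events, severe allergic reaction, neutropenia, symptomatic deterioration and the participant's own decision.

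**Who is analysed.** Section 11.7 includes every randomised participant with confirmed aSAH under the allocated group, whether or not they adhered. Section 11.7.1 gives a complete-case rule for the primary analysis, with multiple imputation as a sensitivity analysis. It does not mention a missing mediator.

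**The concern.** Two features weaken the IL-6 question, which is a stated secondary objective (section 3.3).

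First, the sampling rule makes the mediator missing because of something that happens after randomisation. Some reasons for stopping are likelier on active drug, and others mark a worse prognosis. The people concerned remain in the outcome analysis, so the mediation analysis must drop them or impute the mediator with no post-baseline IL-6 value to work from.

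Second, randomisation protects the comparison of arms but not the path from IL-6 to outcome. Section 1.1.2 says "Plasma IL-6 levels are also associated with poor functional outcome", so IL-6 before treatment is a plausible common cause of day 3-5 IL-6 and of the mRS. It is measured, but the protocol gives it no analytic role.

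At stake is whether a reported indirect effect reflects IL-6 reduction or partly reflects who was ill to begin with and who was sampled.

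**Working it through.** **1. The plan's own figures.** The protocol gives no size or power for the mechanism analysis. The trial size gives the denominator and reproduces: 360/0.9 = 400 per group, or 800 with confirmed aSAH, and 800/0.8 = 1000 randomised.

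**2. Sections 7.7.2, 7.8 and 11.7 side by side, for a participant with confirmed aSAH.**
- On treatment at the day 3-5 draw: mediator yes, outcome yes.
- Withdrawn from treatment after the draw: mediator yes, outcome yes.
- Withdrawn from treatment before the draw: mediator no, IL-1Ra no, outcome yes.

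Only the third group is affected. Section 7.8 also withdraws from treatment anyone whose aneurysm is not confirmed within 72 hours of randomisation. If it is confirmed later, section 11.7 seeks an outcome, while 7.8 describes follow-up only to day 30 and allows no further sample.

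**3. How many.** The documents do not say. Section 2.2 reports 2 of 68 phase II participants on IL-1Ra who withdrew because of injection site reactions: 2/68 = 2.9%, with no timing. If all such withdrawals came before day 3-5, that would be 0.029 × 400, or about 12 in the active arm. An assumed 5% to 15% would be 20 to 60.

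**4. Effect on the IL-6 contrast.** Phase II gave a geometric mean ratio of 0.35 (65% lower, section 1.1.3). Assume a share w of the active arm stops early and then has no IL-6 reduction. The intention-to-treat ratio is 0.35^(1−w):
- w = 0.05: 0.369, a 63% reduction
- w = 0.10: 0.389, a 61% reduction
- w = 0.15: 0.410, a 59% reduction

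The figure among those sampled would be 65%.

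**5. Effect on the indirect effect.** Simulation with 400,000 participants per scenario. B is baseline log IL-6 (SD 1) and A is treatment.
- Mediator: M = rB + ln(0.35)A + √(1−r²)e, where ln(0.35) = −1.05.
- Outcome: logit P(poor) = −1.0 + b_M·M + b_B·B, so there is no direct effect of treatment.
- Indirect odds ratio: exp(a·b), where a is the treatment coefficient in the mediator model and b the mediator coefficient in the outcome model.

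The mediator was made missing in about 6% or 17%, depending on arm and baseline IL-6. With baseline IL-6 in both models, complete-case estimates were 1.00 to 1.01 (truth 1.00) and 0.72 to 0.74 (truth 0.73). Loss that depends only on modelled variables is therefore nearly harmless. Stopping driven by unmeasured early deterioration was not simulated and could bias the result.

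**6. Leaving baseline IL-6 out.** Same simulation, no missing data, true indirect odds ratio 1.00:

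| r | b_B = 0 | b_B = 0.3 | b_B = 0.6 |
|---|---|---|---|
| 0.3 | 1.00 | 0.91 | 0.84 |
| 0.5 | 1.00 | 0.85 | 0.74 |
| 0.7 | 1.00 | 0.80 | 0.65 |

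A hand approximation agrees. Given treatment, M absorbs about r·b_B of the baseline effect, so the indirect odds ratio is about 0.35^(r·b_B). That gives 0.35^0.09 = 0.91 and 0.35^0.42 = 0.64. With baseline IL-6 in both models the estimates return to 1.00 to 1.01. When the true value is 0.73, omission gives 0.48 to 0.73.

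**7. False claims of mediation.** Assume 640 analysed, no causal effect of IL-6 and baseline IL-6 left out.
- Log-odds per SD set equal to the correlation, at 0.3, 0.4 and 0.5: 15%, 41% and 76% of trials (1,500 per scenario).
- Weaker link to outcome (400 per scenario): 7% at correlation 0.3 and log-odds 0.1 (indirect odds ratio 0.97); 10% at 0.3 and 0.2 (0.94); 10% at 0.5 and 0.1 (0.94).
- IL-6 linked to outcome only through a binary grade that is adjusted for: 4% (1.00).
- Baseline IL-6 included, in the scenarios of the first item: 4% to 6%.

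The documents give neither the correlation nor the log-odds.

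**The case against.** **Covariates.** A reader might infer from section 11.5 that the mediation model is adjusted only for the stratification factors. The documents do not support that. The section sets a common adjustment and does not exclude others, and section 11.3 leaves detail to an SAP that is not shown. The covariate list of a mediation model is ordinary SAP content. WFNS band is already adjusted for, and the sliding dichotomy defines success by baseline prognosis, so some confounding may already be absorbed. This objection stands. The covariate part is a recommendation, not an error in the protocol.

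**Sampling.** A reader might infer that the mediator is seen only in people still on drug. That is too broad: anyone who stops after the day 3-5 draw has been sampled. The early-stopping rate is unknown, and if stopping depends on modelled variables the bias is negligible. This also stands and limits the size of the point.

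**Fidelity.** A reader might infer that treatment fidelity is necessarily overstated. It is not, because section 7.7.2 records every administration and section 8.1.3 records omissions, reasons and delivered dose. With the 4-6 hour half-life in section 7.2.1, an IL-1Ra value taken well after stopping says little about allocation, so the sample matters mainly for IL-6.

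The objection does not remove the conflict in data collection. Section 7.8 forgoes a scheduled mediator sample in people whom section 11.7 keeps in the analysis, and no later document can restore it.

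**Conclusion.** The point holds in a limited form. The sampling rule in section 7.8 leaves participants withdrawn before the day 3-5 draw with an outcome but no mediator, for reasons that can relate to treatment and prognosis. The number is unknown and may be small. The bias is near zero if stopping depends only on variables in the model, and could be material if it reflects unmeasured early deterioration.

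The covariate part is an improvement on the one adjustment set the protocol states. Without baseline IL-6, a null indirect odds ratio lies between 1.00 and 0.65 over the assumed ranges (correlation 0.3 to 0.7, log-odds 0 to 0.6 per SD, SD of log IL-6 equal to 1). There is no bias if baseline IL-6 has no effect on outcome beyond its effect through later IL-6.

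It would go too far to say that the mechanism question will be answered with bias, because that needs inputs the documents do not give. The issue concerns a secondary objective and leaves the primary analysis untouched.

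**What to change.** 1. **Section 7.8, reconciled with 7.7.2 and 11.7.** State that the scheduled day 3-5 research sample is still sought after withdrawal from trial treatment, unless the participant or representative declines or the participant is confirmed non-aneurysmal. State also what applies when an aneurysm is confirmed after the 72-hour point. Cost: a short amendment and one blood draw in a few participants who have stopped study drug. The sample is already scheduled, so no new procedure is added.
2. **Section 11.3.4 or the SAP.** Name log baseline IL-6 and baseline prognostic variables, such as age and WFNS grade, in both the mediator and the outcome model. Cost: wording only, since the data are already collected.
3. **SAP.** Say how a missing mediator is handled, report the number withdrawn before the draw by arm and reason, and add a sensitivity analysis for unmeasured mediator-outcome confounding. Cost: analysis time.
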